4.0 Clinical Measurements

Primary

Clinical ratings of pain will be measured by visual analog scales for pain as well as unpleasantness of pain sensation (i.e. “how much pain are you in right now?” and “how much is the pain bothering you right now?”). Patient reports of sensory and pain detection using the Quantitative sensory testing (QST) with the Medoc device will also be used, with and without stimulation.

Physiological measurements related to neural oscillatory activity during various triggered neural recordings with various pain states, activity states, medication states, etc. (~14 recordings per week at home, ~6-8 recordings per in-clinic visit,) will include: wide spectrum power-spectral analysis as well as using specific frequency domain for mean log power (i.e. in the delta, theta, alpha, beta, gamma bands), pain-related changes in broad spectrum power density, and coupling between the phase of low frequency rhythms and broadband gamma amplitude (phase-amplitude coupling, abbreviated PAC) [145-147].

Clinical measures and physiological measurements will be collected and recorded by members of the research and clinical team, as well as from at-home data collection sessions.

Secondary

Measures from Neuropathic Pain Questionnaire, Beck Depression and Anxiety, NIH PROMIS Global health and physical function scales and SF-36 will also be compared from pre-intervention to post Phase 1, phase 2 and phase 3 time points.

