In phase 1, patients will be implanted and undergo long-term ambulatory monitoring of their self-reported pain states along with recordings of LFPs from electrodes implanted in the cingulate and orbitofrontal paired regions (~6 months in duration, time period based on previous pain studies [2, 85], visits 6-10, approximately 1 visit per month, up to 10 visits, if needed). Neural activity from implanted electrodes will be simultaneously recorded, one lead per recording channel. During this time period, neural data in combination with pain state reports will be analyzed in order to identify biomarkers of the pain experience and develop a predictive model of increased pain. Importantly, although recruitment will only include patients who are treatment-resistant to pain medication, patients will likely be on medication regimens for pain relief. These will continue to be managed by the patient’s regular pain management team (i.e. will be independent of this study). We will closely monitor the medication regimen and any changes to the regimen. Patients will be asked to record activities at least 3 days a week at the following times:

- Immediately after waking up in the morning
- 30 mins post medication use
- afternoon between 1200 - 1400 pm
- immediately before bedtime

Also, twice a week, patients will be asked to record during pre-identified activities that exacerbate pain (e.g. bending, climbing stairs, etc.). Patients will also be asked to wear a FitBit or similar activity monitor and upload their anonymized data (i.e. no personal health information shared).

Phase 1 – In-clinic sessions

In clinic sessions will also occur in Phase 1, occurring approximately every 3 weeks, taking the measures of VAS pain, VAS unpleasantness, C-SSRS, BDI/BAI, Neuropathic Pain Questionnaire, NIH PROMIS Global health and physical function scales and SF-36. Baseline LFP recordings will also be taken from ~2 minutes. At the study visits from week 3 onwards, we will also include

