- 5) Stimulation off + anticipatory anxiety task
- 6) Stimulation off + anticipatory anxiety task
- 7) Stimulation off + cognitive-attention task
- 8) Stimulation off + cognitive-attention task
- 9) Stimulation off + naloxone
- 10) Stimulation on + naloxone
- 11) Wash-out, stimulation off period
- 12) LFP recording after painful activity
- 13) Recording after pain medication

Phase 2 will test the effectiveness of closed-loop stimulation in comparison to no-stimulation. In phase 3, the effectiveness of closed-loop stimulation will be tested in comparison to open-loop stimulation settings. If data of sufficiently high quality are collected before the 6-month phase period ends in Phase 2, depending on pain relief symptoms, the research team may accelerate phase 2 to phase 3 before the 6-month period ends to ensure rapid positive clinical outcomes.

Phase 3

In phase 3, patients will continue with at-home stimulation with either personalized closed-loop or traditional open-loop stimulation strategies enacted via their implanted system. Patients will be blinded to the stimulation strategy in which they are assigned. Assignment of open-loop or closed-loop will be randomized and occur in 6-week time periods, with each patient serving as his or her control as to which stimulation treatment is more effective. EEG may be used during this phase for safety, to ensure that subclinical seizure activity is not present during stimulation.

During this phase, patients will be monitored closely, with daily at-home phone calls and frequent in-clinic appointments. This phase of the study will last approximately 1 year (time line based on previous published reports [2, 85, 94], with in-clinic appointments occurring approximately every 6 weeks.

In-clinic appointments will consist of the following:

- 1) VAS pain, VAS unpleasantness, C-SSRS, BDI/BAI, Neuropathic Pain Scale, NIH PROMIS Global health and physical function scales, and SF-36
- 2) Baseline LFP
- 3) Stimulation off + QST (no pain medication)
- 4) Stimulation on + QST
- 5) Stimulation off + anticipatory anxiety task
- 6) Stimulation on + anticipatory anxiety task
- 7) Stimulation off + cognitive-attention task
- 8) Stimulation off + cognitive-attention task
- 9) Stimulation off + naloxone
- 10) Stimulation on + naloxone

- 11) Wash-out, stimulation off period
- 12) LFP recording after painful activity
- 13) Recording after pain medication

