3	Post-operatively, prior to hospital discharge, and during hospitalization	Clinical: follow-up physical prior to discharge Research: Activa Data collection daily, pain assessment daily for clinical characterization, and C-SSRS/BDI/BAI/ NIH PROMIS /NPQ prior to discharge	
4	10 days post implantation (+/- 3 days)	Clinical: follow up physical and staple removal and wound check Research: Teach at-home monitoring, Activa Data collection and C-SSRS/BDI/BAI/ NIH PROMIS /NPQ, (including QST+ baseline LFP recording), recording with painful activity, pain medication	
5	Three weeks post implantation (+/- 7 days) Visit for research only	Clinical: none Research visit only: visit 5 Activa Data collection and C-SSRS/BDI/BAI/ NIH PROMIS /NPQ/SF-36, (including QST), recording with painful activity, pain medication	
6	Two Months (+/- 10 days)	Clinical: HEAD CT for stability Research: Activa Data collection and C-SSRS/BDI/BAI/ NIH PROMIS /NPQ/SF-36, (including QST+baseline LFP recording), recording with painful activity, pain medication	
7	Three Months (+/- 10 days);	Clinical: none Research visit only: Activa Data collection and C-SSRS/BDI/BAI/ NIH PROMIS /NPQ/SF-36, (including QST+baseline LFP recording), recording with painful activity, pain medication	
8-10	Every 4 weeks	Clinical: visits 8 and 10: History and Physical at 4 month and 6 mo. Research: visits 8, 9, 10: Activa Data collection and C-SSRS/BDI/BAI/ NIH PROMIS /NPQ, SF-36 (including QST+baseline LFP recording), recording with painful activity, pain medication	
11-24	Every day for 2 weeks, stimulation optimizing (START PHASE 2)	Clinical only: visits 11-24 DBS programming initial and revisits if needed.; Research: 11 and 24 visit: C-SSRS/BDI/BAI	Phase 2: Months 7-12; Daily visits for 2 weeks followed by 7 study visits
25-31	every 3 weeks for closed loop randomization	Clinical: visit 28 only; History and Physical for stability Research: visits 25-31; Activa Data collection and VAS scores before and during stimulation, including QST+baseline LFP recording, recording with painful activity, pain medication. C-SSRS/BDI/BAI/ NIH PROMIS /NPQ, SF-36. DBS on/ off	

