V10:01.2019	(Every 6 weeks, +/- 10 days), Months 13-24 (PHASE 3)	Clinical: visit 32 and 36 and final visit of study: H&P for stability Research: visits 32-41: Activa Data collection and VAS scores before and during stimulation, (including QST+baseline LFP recording), recording with painful activity, pain medication; (including QST), recording with painful activity, pain medication. C-SSRS/BDI/BAI/ NIH PROMIS /NPQ, SF-36. DBS open vs closed Final Research visit: Post-intervention Neuropsychological / Behavioral testing	Phase 3: Months 13-24; visit every 6 weeks, 8-10 visits

*Abbreviation: C-SSRS=Columbia Suicide Severity Rating Scale; BDI=Beck Depression Inventory; BAI=Beck Anxiety Inventory.

Progression of phases: We anticipate approximately 6 months for phase 1, a time period based on previous studies [2, 85]. As phase 2 may provide a potential for therapeutic relief of pain symptoms, if patients' pain signatures are reliably detected in a shorter time period in phase 1, the patient may opt to proceed to phase 2 at an earlier time point (i.e. fewer sessions for phase 1). If data of sufficiently high quality is collected before the 6 month phase period ends in Phase 2, depending on pain relief symptoms, the research team may accelerate phase 2 to phase 3 before the 6-month period ends to ensure rapid positive clinical outcomes (in which longer pain relief may occur).

In certain patients who do not experience a sufficiently wide range of pain fluctuation scores (ie. Pain ranges always from 8-9 /10) , it may be difficult to create a predictive model of pain from neural data during phase 1. In these cases, we may opt to proceed to phase 2 at an earlier time point, as soon as 6 weeks post-implantation. Using potentially therapeutic stimulation of ACC or OFC to decrease pain scores at the start of phase 2, we can then aim to calculate biomarkers of pain relief and elevated pain states at the start of phase 2 during stimulation optimization. Additionally, if in phase 1 we anticipate difficulty in successfully collecting biomarker information for any reason, we may opt to progress to phase 2 at an earlier time point to support a positive clinical outcome for the patient.

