6.0 Statistical Methods and Data Analysis

Ratings of pain will be measured by visual analog scales for pain as well as unpleasantness of pain sensation (i.e. “how much pain are you in right now?” and “how much is the pain bothering you right now?”). Patient reports of sensory and pain detection using the Quantitative sensory testing (QST) with the Medoc device will also be used, with and without stimulation.

In Phase 2, patients will serve as their own controls in a single-blinded phase (6-months in duration) in which placebo versus active open-loop stimulation is used. During this 6-month period, four sham and four active stimulation periods will occur in a random, blinded assignment. During the 8 in-clinic visits, the threshold for sensory and pain detection with the Medoc device will be used and scores will be compared for each patient during sham versus active stimulation periods in one-sample, two-tailed t-test. The 10 patients’ sham versus stimulation scores will also be used in group analysis to test the effects of open-loop and closed-loop stimulation.

In Phase 2, the visual analog scale scores recorded during the at-home recording sessions for various activities will be compared for each patient [(see Figure 3; 168 scores for sham sessions and 168 scores for active stimulation sessions, per patient); (i.e. 3 times per week for 4 activities and 2 times per week for at least 1 painful activity, for at least 14 VAS scores per week; 24 weeks total with 3 weeks per session-sham or stimulation, 8 sessions total, 4 sham sessions and 4 stimulation sessions)].

Multiple regression analysis of all patients will also be used to test for effects of stimulation on various activities, time of day, stimulation effects over time in trial and potential differences in stimulation effects on pain etiologies (i.e. spinal cord injury versus phantom limb versus post-stroke).

Phase 1 (no-intervention) VAS scores will be compared to Phase 2 (sham controlled and active stimulation) VAS scores.

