LFP data will be analyzed using wide spectrum power-spectral analysis as well as using specific frequency domain for mean log power (i.e. in the delta, theta, alpha, beta, gamma bands). We will also examine coherence and cross-frequency coupling between the channels [145-147]. Using a repeated measures ANOVA statistical analysis, summary statistics for power in relevant frequency bands, pain-related power changes, and indices of phase-amplitude coupling will be compared at different time points, different DBS conditions (on and off), possible medication states (on and off) and different pain states. Although the sample size is small, we will assess the correlation between pain and non-pain states with brain physiology measures, and clinical instruments used to measure pain relief produced by DBS. Additionally, bootstrapping statistical applications (i.e. a Monte Carlo algorithm) and general linear mixed models can be utilized to investigate potential statistical effects, given the small sample size.

Neural activity will be compared during pain states, activity states, medication states, etc. for Phase 1 (no-intervention), as well as Phase 2 (sham controlled and open-loop stimulation) and Phase 3 (open-loop stimulation and closed-loop stimulation).

Sample size calculation: This is a pilot study consisting of existing chronic brain recording technology. The goals are to provide pain relief strategies using the Activa PC+S neural interface, as well as assess feasibility and to collect data that will be used to inform treatment plans using DBS mechanisms. Thus, there is no formal sample size calculation. However, the study is designed such that patients will serve as their own controls in a blinded, placebo versus active open-loop stimulation design, with multiple periods of placebo versus active stimulation. Patients will also serve as their own controls in open-loop versus closed-loop stimulation, in a randomly assigned, blinded, multiple 6-week time periods of open-loop versus closed-loop stimulation. At-home recording sessions will also be utilized to increase the number of testing samples per patient over the trial. In this manner, the statistical power is increased to show treatment efficacy in either of these phases.

Criteria for study success that would justify a larger subsequent trial: This study will be considered to justify a larger subsequent trial if we can demonstrate that:

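### NPQ, BDI, BAI, PROMIS and SF-36 get only a pre-intervention to post-phase comparison; no ON-versus-OFF or open-versus-closed contrast is tied to them, though they are collected in the randomised periods

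*Combined protocol and SAP*

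**What the plan says.** Section 4.0 (Clinical Measurements, Secondary) lists NPQ, the two Beck inventories, PROMIS and SF-36 and closes: "SF-36 will also be compared from pre-intervention to post Phase 1, phase 2 and phase 3 time points". It names no test and does not define the post time points. The synopsis lists NPQ, PROMIS and SF-36 as secondary efficacy endpoints and puts the Beck inventories under safety.

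The Protocol Chart in section 3.0 schedules all five scales at the Phase 2 randomised visits, 25 to 31 ("C-SSRS/BDI/BAI/ NIH PROMIS /NPQ, SF-36. DBS on/ off"), and at the six-weekly Phase 3 visits ("C-SSRS/BDI/BAI/ NIH PROMIS /NPQ, SF-36. DBS open vs closed").

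Section 6.0 states that in Phase 2 "four sham and four active stimulation periods will occur in a random, blinded assignment". It also plans a regression ("Multiple regression analysis of all patients will also be used to test for effects of stimulation on various activities") without naming its outcome, and says that "general linear mixed models can be utilized to investigate potential statistical effects, given the small sample size".

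On what else may move the scores, section 1.0 leaves pain medication with each patient's own team and says only: "We will closely monitor the medication regimen and any changes to the regimen". On the end of Phase 2, it says that, given data of sufficient quality, "depending on pain relief symptoms, the research team may accelerate phase 2 to phase 3 before the 6-month period ends".

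**The concern.** Phases 2 and 3 are built as repeated randomised periods with each patient as his or her own control. For these five scales the stated comparison does not use that randomisation. A change from before surgery to the end of Phase 2 or 3 contains the stimulation effect, but also anything else that changed over 12 or 24 months and any placebo response. It also depends on which stimulation state the patient was in when the post value was taken, which the plan does not fix.

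As written, a change on these scales at the end of Phase 2 or 3 could not be attributed to stimulation in either direction. Drift or placebo response could read as benefit, and OFF-state values could dilute a real effect. The data for a randomised comparison are already scheduled.

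**Working it through.** **1. Which outcome each planned analysis names**

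| Analysis | Outcome named | By stimulation state? |
|---|---|---|
| 4.0, pre to post each phase | NPQ, BDI, BAI, PROMIS, SF-36 | No |
| 6.0, per-patient t-test, Phases 2 and 3 | QST thresholds | Yes |
| 6.0, group analysis | None; follows the QST sentence | Yes |
| 6.0, home-score comparison | VAS | Yes |
| 6.0, multiple regression | None; follows the VAS paragraph | Yes |
| 6.0, comparison between phases | VAS | No |
| 6.0, repeated-measures ANOVA | LFP measures | Yes |
| 6.0, correlation with brain physiology | Instruments measuring pain relief, not listed | No (association) |
| 6.0, bootstrap and mixed models | None; optional | Not stated |

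Every stimulation contrast that names an outcome is for QST, home VAS or LFP.

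**2. What each change contains**

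Let m be the implantation effect; g1 and g2 the drift (including medication changes) by the end of Phases 1 and 2; p the placebo response; d the stimulation effect; and Z = 1 if the post Phase 2 value is taken ON, otherwise 0.

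- Post Phase 1 minus pre = m + g1, because stimulation is not enabled in Phase 1.
- Post Phase 2 minus pre = m + g2 + p + Zd.
- Post Phase 2 minus post Phase 1 = (g2 − g1) + p + Zd.
- Within-patient ON minus OFF = d in expectation. Random order balances drift, and p cancels if blinding holds and carryover is absent.

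The post Phase 1 point therefore removes implantation and early drift. It leaves later drift, placebo response and the final state.

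**3. The final state**

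Inputs from section 6.0: four sham and four active periods in random order. Reading the post value as the last visit of a completed Phase 2, P(Z = 1) = 4/8 = 0.5, so the expected change is d/2 plus all shared terms.

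If the 10 patients are randomised independently, P(3 to 7 end ON) = (120 + 210 + 252 + 210 + 120)/1024 = 912/1024 = 0.89. In most realisations the mean would carry 30% to 70% of a common d.

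If the post value is instead the average over eight Phase 2 visits, it carries (4d + 4 × 0)/8 = d/2 in every patient. The dilution is the same, but the random mixing goes.

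**4. Precision (illustrative only; the estimands differ)**

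Assume a visit SD of 1 and an effect that does not vary between patients.

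- ON minus OFF: variance 1/4 + 1/4 = 0.5, signal-to-noise d/0.707 = 1.41d.
- Pre versus the Phase 2 average: variance 1 + 1/8 = 1.125, signal d/2, so 0.5d/1.061 = 0.47d. The ratio is 3.0.
- Pre versus one last visit in a random state: variance 2 + d²/4. At d = 0.5 this gives 0.25/1.436 = 0.174 against 0.5/0.707 = 0.707, a ratio of 4.06.
- If every last visit were ON: d/1.414 = 0.707d, a ratio of 2.0.

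With n = 10 and an assumed two-sided 5% level, a paired t-test on one mean difference per patient has 80% power only for a standardised difference of about 1.00. Any contrast added here is for estimation.

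**5. Early exit**

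Section 1.0 lets Phase 2 end early depending on pain relief, with no numeric rule and no direction. An illustrative simulation in which patients leave after a low-pain visit moves the post Phase 2 change 0.07 to 0.62 visit SDs towards benefit, with no true effect and no drift. Letting them leave after a high-pain visit moves it about 0.06 to 0.61 towards harm. The sign comes from the assumed rule.

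**6. Can scores be assigned to periods?**

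- Visits 25 to 31 make 31 − 25 + 1 = 7 (section 3.0). Section 6.0 has 24/3 = 8 periods and eight in-clinic visits.
- Section 6.0 describes Phase 3 as closed-loop versus open-loop, then speaks of sham and active periods.
- The session lists in section 1.0 for Phases 2 and 3 name a Neuropathic Pain Scale; sections 3.0 and 4.0 name the Neuropathic Pain Questionnaire.

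**The case against.** The strongest reply is that the plan does not rule out a stimulation contrast. The regression and the group analysis name no outcome, and the mixed models could be applied to any scale. That stands as far as it goes: a reader might infer that the contrast is excluded, and the documents do not say so. But an analysis that names no scale and follows QST or VAS text does not specify one, while section 4.0 does specify the pre-post comparison.

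Second, a reader might infer that the pre-post comparison separates nothing. That is too strong. The post Phase 1 point follows about six months implanted with stimulation off, and isolates implantation plus early drift.

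Third, a reader might infer that early exit biases the result towards benefit. The documents do not support a direction. Acceleration also requires good data, and poor relief could prompt the move as readily as good relief. What stands is that the last visit may depend on outcome.

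Fourth, the plural time points in section 4.0 could mean several visits per phase. Averaging would remove the random final state, though not the dilution by half or the drift.

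Two further inferences should be left aside. The unnumbered Phase 2 and 3 bullets in section 3.0 place the scales after stimulation testing, but those bullets are not chronological, and every numbered session list puts the scales first. The figures of up to ten visits, and of visits to 34 if needed, are ceilings; the real mismatch is 7 against 8.

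Finally, this is a pilot without a formal sample size, and the pre-post comparison carries no named test. That limits the weight and does not remove the point.

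**Conclusion.** The point holds. The one comparison specified for these five scales is uncontrolled, and no randomised contrast is tied to them although the data for one are scheduled. The post Phase 2 and post Phase 3 changes cannot be attributed to stimulation.

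The size depends on how the post value is read. As the last visit of a completed Phase 2, or as the average of eight balanced visits, it carries an expected d/2 plus all shared drift and placebo response. This assumes the four-and-four allocation in section 6.0 is carried out in full. The precision ratios and the early-exit figures rest on assumed variances and exit rules, and the conclusion does not depend on them.

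The weight is minor to moderate. NPQ, PROMIS and SF-36 are secondary. BDI and BAI also serve safety, where change from baseline is a natural summary. None of the five is named in the success criteria that close section 6.0.

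**What to change.** In section 4.0, for attributing effects on these scales to stimulation, specify:

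- the within-patient ON-minus-OFF contrast in Phase 2 and the closed-minus-open contrast in Phase 3, from all randomised-period visits;
- assignment of each score to the period just ended;
- the patient as the unit, for example a mixed model with patient and patient-by-state terms, plus a period or time term because Phase 2 may end early depending on pain relief;
- estimates with intervals, not confirmatory tests.

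Keep the pre-to-post-phase change as descriptive, and for BDI/BAI safety monitoring. Define the post visit and report the stimulation state at each one.

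So that scores can be assigned, reconcile the 7 Phase 2 visits in section 3.0 with the 8 in section 6.0, the Phase 3 sham wording with its open-versus-closed design, and Neuropathic Pain Scale with Neuropathic Pain Questionnaire.

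The cost is SAP wording and modest analysis work; no new data are needed. There are downsides. Carryover, or a recall window longer than a three-week period (the documents give no recall windows), would shrink the contrast. The contrast cannot show an implantation effect, so the pre-to-post Phase 1 change is still needed. It also adds secondary estimates in 10 patients.
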